
ATTACHMENTS**Attachment 1: Division of Microbiology and Infectious Diseases (DMID)
Pediatric Toxicity Tables (November 2007; draft)**

**DIVISION OF MICROBIOLOGY AND INFECTIOUS
DISEASES (DMID) PEDIATRIC TOXICITY TABLES
NOVEMBER 2007
DRAFT²³**

ABBREVIATIONS: Abbreviations utilized in the Table:

ULN Upper Limit of Normal

LLN Lower Limit of Normal

Rx Therapy

Req Required

Mod Moderate

IV Intravenous

ADL Activities of Daily Living

Dec Decreased

ESTIMATING SEVERITY GRADE

For abnormalities NOT found elsewhere in the toxicity tables use the scale below to estimate grade of severity:

GRADE 1	Mild: Transient or mild discomfort (<48 hours); no medical intervention/therapy required
GRADE 2	Moderate: Mild to moderate limitation in activity - some assistance may be needed; no or minimal medical intervention/therapy required
GRADE 3	Severe: Marked limitation in activity, some assistance usually required; medical intervention/therapy required, hospitalizations possible
GRADE 4	Life-threatening or death*: Extreme limitation in activity, significant assistance required; significant medical intervention/therapy required, hospitalization or hospice care probable

* The draft DMID pediatric toxicity tables characterize death as a Grade 5 event, for the purposes of this study the sponsor will categorize events into 4 grades and has included death with life-threatening in the Grade 4 category.

SERIOUS OR LIFE-THREATENING ADVERSE EVENTS

ANY clinical event deemed by the clinician to be serious or life-threatening should be considered a Grade 4 event. Clinical events considered to be serious or life-threatening include, but are not limited to: seizures, coma, tetany, diabetic ketoacidosis, disseminated intravascular coagulation, diffuse petechiae, paralysis, acute psychosis, severe depression.

COMMENTS REGARDING THE USE OF THESE TABLES

- Standardized and commonly used toxicity tables (Division of AIDS, NCI's Common Toxicity Criteria [CTC], and WHO) have been adapted for use by the DMID and modified to better meet the needs of participants in DMID trials.
- For parameters not included in the following toxicity tables, sites should refer to the “Guide For Estimating Severity Grade” located above.
- Criteria are generally grouped by body system.
- Some protocols may have additional protocol-specific grading criteria, which will supersede the use of these tables for specified criteria.

**DIVISION OF MICROBIOLOGY AND INFECTIOUS
DISEASES (DMID) PEDIATRIC TOXICITY TABLES
NOVEMBER 2007**

(Selected Values for children less than or equal to 3 months of age – does not apply to preterm infants)

**For all parameters not listed in this table, please refer to
the DMID Toxicity Table for children >3 months of age**

HEMATOLOGY				
	Grade 1	Grade 2	Grade 3	Grade 4
Hemoglobin				
1-7 days old	13.0-14.0 g/dL	12.0-12.9 g/dL	<12 g/dL	Cardiac Failure secondary to Anemia
8-21 days old	12.0-13.0 g/dL	10.0-11.9 g/dL	<10.0 g/dL	Cardiac Failure secondary to Anemia
22-35 days old	9.5-10.5 g/dL	8.0-9.4 g/dL	<8.0 g/dL	Cardiac Failure secondary to Anemia
36-60 days old	8.5-9.4 g/dL	7.0-8.4 g/dL	<7.0 g/dL	Cardiac Failure secondary to Anemia
61-90 days old	9.0-9.9 g/dL	7.0-8.9 g/dL	<7.0 g/dL	Cardiac Failure secondary to Anemia
Absolute Neutrophil Count				
1 day old	5000-7000/mm ³	3000-4999/mm ³	1500-2999/mm ³	<1500/mm ³
2-6 days old	1750-2500/mm ³	1250-1749/mm ³	750-1249/mm ³	<750/mm ³
7-60 days old	1200-1800/mm ³	900-1199/mm ³	500-899/mm ³	<500/mm ³
61-90 days old	750-1200/mm ³	400-749/mm ³	250-399/mm ³	<250/mm ³

**DIVISION OF MICROBIOLOGY AND INFECTIOUS
DISEASES (DMID) PEDIATRIC TOXICITY TABLES
NOVEMBER 2007**

(Selected values for children younger than or aged 3 months)

HEMATOLOGY (continued)				
	Grade 1	Grade 2	Grade 3	Grade 4
Bilirubin (fractionated bilirubin test must be performed when total bilirubin is elevated)				
<7 days old	-	20-25mg/dL	26-30 mg/dL	>30 mg/dL
7-60 days old	1.1-1.9xN	2.0-2.9xN	3.0-7.5xN	>7.5xN
61-90 days old	1.1-1.9xN	2.0-2.9xN	3.0-7.5xN	>7.5xN
Creatinine				
<7 days old	1.0-1.7 mg/dL	1.8-2.4 mg/dL	2.5-3.0 mg/dL	>3.0 mg/dL
7-60 days old	0.5-0.9 mg/dL	1.0-1.4 mg/dL	1.5-2.0 mg/dL	>2.0 mg/dL
61-90 days old	0.6-0.8 mg/dL	0.9-1.1 mg/dL	1.2-1.5 mg/dL	>1.5 mg/dL
Creatinine Clearance				
<7 days old	35-40 mL/min	30-34 mL/min	25-29 mL/min	<25 mL/min
7-60 days old	45-50 mL/min	40-44 mL/min	35-39 mL/min	<35 mL/min
61-90 days old	60-75 mL/min	50-59 mL/min	35-49 mL/min	<35 mL/min
Hypocalcemia				
<7 days old	6.5-6.9 mEq/L	6.0-6.4 mEq/L	5.5-5.9 mEq/L	<5.5 mEq/L
7-60 days old	7.6-8.0 mEq/L	7.0-7.5 mEq/L	6.0-6.9 mEq/L	<6.0 mEq/L
61-90 days old	7.8-8.4 mEq/L	7.0-7.7 mEq/L	6.0-6.9 mEq/L	<6.0 mEq/L
Hypercalcemia				
<7 days old	12.0-12.4 mEq/L	12.5-12.9 mEq/L	13.0-13.5 mEq/L	>13.5 mEq/L
7-60 days old	10.5-11.2 mEq/L	11.3-11.9 mEq/L	12.0-13.0 mEq/L	>13.0 mEq/L
61-90 days old	10.5-11.2 mEq/L	11.3-11.9 mEq/L	12.0-13.0 mEq/L	>13.0 mEq/L

**DIVISION OF MICROBIOLOGY AND INFECTIOUS
DISEASES (DMID) PEDIATRIC TOXICITY TABLES**
NOVEMBER 2007
(Older than 3 months of age)

LOCAL REACTIONS				
	Grade 1	Grade 2	Grade 3	Grade 4
Induration	<10 mm	10-25 mm	26-50 mm	>50 mm
Erythema	<10 mm	10-25 mm	26-50 mm	>50 mm
Edema	<10 mm	10-25 mm	26-50 mm	>50 mm
Rash at Injection Site	<10 mm	10-25 mm	26-50 mm	>50 mm
Pruritus	Slight itching at injection site	Moderate itching at injection extremity	Itching at injection extremity and other sites	Itching over entire body

HEMATOLOGY				
	Grade 1	Grade 2	Grade 3	Grade 4
Hemoglobin for children older than 3 months and younger than 2 years of age	9.0 - 9.9 g/dL	7.0 - 8.9 g/dL	<7.0 g/dL	Cardiac Failure secondary to anemia
Hemoglobin for children older than 2 years of age	10 - 10.9 g/dL	7.0 - 9.9 g/dL	<7.0 g/dL	Cardiac Failure secondary to anemia
Absolute Neutrophil Count	750 - 1200/mm ³	400 - 749/mm ³	250 - 399/mm ³	<250/mm ³
Platelets	-----	50,000 - 75,000/mm ³	25,000 - 49,999/mm ³	<25,000/mm ³
Prothrombin Time (PT)	1.1 - 1.2 x ULN	1.3 - 1.5 x ULN	1.6 - 3.0 x ULN	>3.0 x ULN
Partial Thromboplastin Time (PTT)	1.1 - 1.6 x ULN	1.7 - 2.3 x ULN	2.4 - 3.0 x ULN	>3.0 x ULN

**DIVISION OF MICROBIOLOGY AND INFECTIOUS
DISEASES (DMID) PEDIATRIC TOXICITY TABLES**
NOVEMBER 2007
(Older than 3 months of age)

GASTROINTESTINAL				
	Grade 1	Grade 2	Grade 3	Grade 4
Bilirubin (when accompanied by any increase in other liver function test)	1.1 - <1.25 x ULN	1.25 - <1.5 x ULN	1.5 - 1.75 x ULN	>1.75 x ULN
Bilirubin (when other liver function are in the normal range)	1.1 - <1.5 x ULN	1.5 - <2.0 x ULN	2.0 - 3.0 x ULN	>3.0 x ULN
AST (SGOT)	1.1 - <2.0 x ULN	2.0 - <3.0 x ULN	3.0 - 8.0 x ULN	>8 x ULN
ALT (SGPT)	1.1 - <2.0 x ULN	2.0 - <3.0 x ULN	3.0 - 8.0 x ULN	>8 x ULN
GGT	1.1 - <2.0 x ULN	2.0 - <3.0 x ULN	3.0 - 8.0 x ULN	>8 x ULN
Pancreatic Amylase	1.1 - 1.4 x ULN	1.5 - 1.9 x ULN	2.0 - 3.0 x ULN	>3.0 x ULN
Uric Acid	7.5 - 9.9 mg/dL	10 - 12.4 mg/dL	12.5 - 15.0 mg/dL	>15.0 mg/dL
CPK	See Neuromuscular Toxicity			
Appetite	-	Decreased appetite	Appetite very decreased, no solid food taken	No solid or liquid taken
Abdominal Pain	Mild	Moderate- No Treatment Needed	Moderate- Treatment Needed	Severe- Hospitalized for treatment
Diarrhea	Slight change in consistency and/or frequency of stools	Liquid stools	Liquid stools greater than 4x the amount or number normal for this child	Liquid stools greater than 8x the amount or number normal for this child

**DIVISION OF MICROBIOLOGY AND INFECTIOUS
DISEASES (DMID) PEDIATRIC TOXICITY TABLES**
NOVEMBER 2007
(Older than 3 months of age)

GASTROINTESTINAL (continued)				
	Grade 1	Grade 2	Grade 3	Grade 4
Constipation	Slight change in the consistency/frequency of stool	Hard, dry stools with a change in frequency	Abdominal pain	Distention and Vomiting
Nausea	Mild	Moderate-Decreased oral intake	Severe-Little oral intake	Unable to ingest food or fluid for more than 24 hours
Vomiting	1 episode/day	2-3 episodes per day	4-6 episodes per day	Greater than 6 episodes per day or Intractable Vomiting

**DIVISION OF MICROBIOLOGY AND INFECTIOUS
DISEASES (DMID) PEDIATRIC TOXICITY TABLES**
NOVEMBER 2007
(Older than 3 months of age)

ELECTROLYTES				
	Grade 1	Grade 2	Grade 3	Grade 4
CREATININE				
Note: ULN are the adult ULN				
3 months - 2 years of age	0.6 - 0.8 x ULN	0.9 - 1.1 x ULN	1.2 - 1.5 x ULN	>1.5 x ULN
2 years - 12 years of age	0.7 - 1.0 x ULN	1.1 - 1.6 x ULN	1.7 - 2.0 x ULN	>2.0 x ULN
Older than 12 years of age	1.0 - 1.7 x ULN	1.8 - 2.4 x ULN	2.5 - 3.5 x ULN	>3.5 x ULN
Hypernatremia	-	<145 - 149 mEq/L	150 - 155 mEq/L	>155 mEq/L or abnormal sodium AND mental status changes
Hyponatremia	-	130 - 135 mEq/L	129 - 124 mEq/L	<124 mEq/L or abnormal sodium AND mental status changes
Hyperkalemia	5.0 - 5.9 mEq/L	6.0 - 6.4 mEq/L	6.5 - 7.0 mEq/L	>7.0 mEq/L or abnormal potassium AND cardiac arrhythmia
Hypokalemia	3.0-3.5 mEq/L	2.5-2.9 mEq/L	2.0-2.4 mEq/L	<2.0 mEq/L or abnormal potassium AND cardiac arrhythmia
Hypercalcemia	10.5 - 11.2mg/dL	11.3 - 11.9 mg/dL	12.0 - 12.9 mg/dL	>13.0 mg/dL
Hypocalcemia	7.8 - 8.4 mg/dL	7.0 - 7.7 mg/dL	6.0 - 6.9 mg/dL	<6.0 mg/dL
Hypomagnesemia	1.2 - 1.4 mEq/L	0.9 - 1.1 mEq/L	0.6 - 0.8 mEq/L	<0.6 mEq/L or abnormal magnesium AND cardiac arrhythmia
Hypoglycemia	55 - 65 mg/dL	40 - 54 mg/dL	30 - 39 mg/dL	<30 mg/dL or abnormal glucose AND mental status changes

Hyperglycemia	116 - 159 mg/dL	160 - 249 mg/dL	250 - 400 mg/dL	>400 mg/dL or ketoacidosis
Proteinuria	Tr-1+ or <150 mg/day	2+ or 150-499 mg/day	3+ or 500-1000 mg/day	4+ or Nephrotic syndrome >1000 mg/day
Hematuria	Microscopic <25 cells/hpf	Microscopic >25 cells/hpf	----	Gross hematuria

**DIVISION OF MICROBIOLOGY AND INFECTIOUS
DISEASES (DMID) PEDIATRIC TOXICITY TABLES**
NOVEMBER 2007
(Older than 3 months of age)

CENTRAL NERVOUS SYSTEM (CNS)				
	Grade 1	Grade 2	Grade 3	Grade 4
Generalized CNS Symptoms	-	-	Dizziness	Hypotonic, hyporesponsive episodes; Seizures; Apnea/Bradycardia; Inconsolable crying >3 hrs;
Headache	Mild	Moderate, Responds to non-narcotic analgesia	Moderate to Severe, Responds to narcotic analgesia	Intractable
Level of Activity	-	Slightly irritable OR slightly subdued	Very irritable OR Lethargic	Inconsolable OR Obtunded
Visual	-	Blurriness, diplopia, or horizontal nystagmus of <1 hour duration, with spontaneous resolution	More than 1 episode of Grade 2 symptoms per week, or an episode of Grade 2 symptoms lasting more than 1 hour with spontaneous resolution by 4 hours or vertical nystagmus	Decrease in visual acuity, visual field deficit, or oculogyric crisis
Myelopathy	-	None	None	Myelopathic/spina 1 cord symptoms, such as: pyramidal tract weakness and disinhibition, sensory level, loss of proprioception, bladder/bowel dysfunction

**DIVISION OF MICROBIOLOGY AND INFECTIOUS
DISEASES (DMID) PEDIATRIC TOXICITY TABLES**
NOVEMBER 2007
(Older than 3 months of age)

PERIPHERAL NERVOUS SYSTEM				
	Grade 1	Grade 2	Grade 3	Grade 4
Neuropathy/ Lower Motor Neuropathy	-	Mild transient Paresthesia only	Persistent or progressive paresthesias, burning sensation in feet, or mild dysesthesia; no weakness; mild to moderate deep tendon reflex changes; no sensory loss	Onset of significant weakness, decrease or loss of DTRs, sensory loss in "stocking glove" distribution, radicular sensory loss, multiple cranial nerve involvement; bladder or bowel dysfunction, fasciculations, respiratory embarrassment from chest wall weakness.
Myopathy or Neuromuscular Junction Impairment	Normal or mild (<2 x ULN) CPK elevation	Mild proximal weakness and/or atrophy not affecting gross motor function. Mild myalgias, +/- mild CPK elevation (<2 x ULN)	Proximal muscle weakness and/or atrophy affecting motor function +/- CPK elevation; or severe myalgias with CPK >2 x ULN;	Onset of myasthenia-like symptoms (fatigable weakness with external, variable ophthalmoplegia and/or ptosis), or neuromuscular junction blockade (acute paralysis) symptoms

**DIVISION OF MICROBIOLOGY AND INFECTIOUS
DISEASES (DMID) PEDIATRIC TOXICITY TABLES**
NOVEMBER 2007
(Older than 3 months of age)

OTHER				
	Grade 1	Grade 2	Grade 3	Grade 4
Allergy	Pruritus without Rash	Pruritic Rash	Mild Urticaria	Severe Urticaria Anaphylaxis, Angioedema
Drug Fever (Rectal)	-	38.5 - 40.0°C 101.3 – 104.0 °F	Greater than 40.0°C Greater than 104.0°F	Sustained Fever: Equal or greater than 40.0°C (104.0°F) for longer than 5 days
Cutaneous	Localized rash	Diffuse maculopapular Rash	Generalized urticaria	Stevens-Johnson Syndrome or Erythema multiforme
Stomatitis	Mild discomfort	Painful, difficulty swallowing, but able to eat and drink	Painful: unable to swallow solids	Painful: unable to swallow liquids; requires IV fluids
Clinical symptoms not otherwise specified in this table	No therapy; monitor condition	May require minimal intervention and monitoring	Requires medical care and possible hospitalization	Requires active medical intervention, hospitalization, or hospice care
Laboratory values not otherwise specified in this table	Abnormal, but requiring no immediate intervention; follow	Sufficiently abnormal to require evaluation as to causality and perhaps mild therapeutic intervention, but not of sufficient severity to warrant immediate changes in study drug	Sufficiently severe to require evaluation and treatment, including at least temporary suspension of study drug	Life-threatening severity; Requires immediate evaluation, treatment, and usually hospitalization; Study drug must be stopped immediately and should not be restarted until the abnormality is clearly felt to be caused by some other mechanism that study drug

Attachment 2: Cardiovascular Safety – Abnormalities**Electrocardiogram**

All important abnormalities from the ECG readings will be listed.

Parameter (unit)	Age class	Abnormally low	Abnormally high
PR (msec)	0 - 2 years	NA	>150
	2 - <3 years	<100	>150
QRS (msec)	0 - 2 years	NA	>79
	2 - <3 years	<40	>79
QT (msec)	0 - 2 years	NA	>500
	2 - <18 years	<320	>450
RR (msec)	0 - 3 months	<333	>750
	3 - 12 months	<400	>860
	1 - 2 years	<430	>1000
	2 - <18 years	<600	>1200

Vital Signs

Normal ranges:

Parameter (unit)	Age class				
	0 – 3 months	3 – 6 months	6 – 12 months	1 – 2 years	2- <3 years
Diastolic BP (mmHg)	45 - 55	50 - 65	55 - 65	55 - 70	45 - 60
Systolic BP (mmHg)	65 - 85	70 - 80	80 - 100	90 - 105	85 - 100
Heart rate HR (bpm)	100 - 150	90 - 120	80 - 120	70 - 110	95 - 125
Respiratory rate	35 - 55	30 - 45	25 - 40	20 - 30	22 - 30
Oxygen saturation SpO ₂ (%)	≥96	≥96	≥96	≥96	≥96

The following clinically relevant abnormalities, measured at rest, will be defined for vital signs:

Parameter (unit)		Age class			
		0 – 3 months	3 – 12 months	1 - 2-years	2- <3 years
Diastolic BP (mmHg)	abnormally low	<35	<40	<40	<40
	abnormally high	>65	>85	>90	>70
Systolic BP (mmHg)	abnormally low	<60	<60	<75	<80
	abnormally high	>110	>110	>120	>110
Heart rate HR (bpm)	abnormally low	<80	<70	<60	<90
	abnormally high	>180	>150	>140	>130
Respiratory rate	abnormally low	<25	<20	<18	<20
	abnormally high	>70	>60	>50	>35
Oxygen saturation SpO ₂ (%)	abnormally low	<92	<92	<92	<92

References:

<http://www.pinterest.com/pin/396316835929288711/>

<http://www.docstoc.com/docs/88983719/Pediatric-Vital-Signs>

<http://www.coheadquarters.com/PennLibr/MyPhysiology/Appendix/AppendVital1.htm>

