The effects on cardiovascular variables will be evaluated by means of descriptive statistics and frequency tabulations. These tables will include observed values and changes from baseline values at each selected timepoint (the screening ECG will be used as baseline). Frequency tabulations of the abnormalities will be generated.

The ECG variables that will be presented are heart rate, PR interval, QRS interval, QT interval, QTcF, and QTcB.

The percentage of subjects with abnormalities will be tabulated.

Changes from baseline results will be presented in pre- versus post-treatment cross-tabulations (with classes for below, within, and above normal ranges).

Vital Signs

Descriptive statistics of body temperature, heart rate, respiratory rate, SBP, DBP, and SpO₂ values and changes from baseline will be summarized at each scheduled timepoint. The percentage of subjects with values beyond clinically relevant limits (as defined in the SAP) will be summarized.

Physical Examination

Physical examination findings will be summarized at each scheduled time point.

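### Attachment 2's heart-rate limits for ages 2 to <3 years conflict with the 1-2 year column and with the attachment's own ECG RR limits

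*Protocol*

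**What the plan says.** Attachment 2 of the protocol has three tables that bear on heart rate.

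- **Normal ranges for vital signs**, for 0-3 months, 3-6 months, 6-12 months, 1-2 years and 2 to <3 years: "Heart rate HR (bpm) 100 - 150 90 - 120 80 - 120 70 - 110 95 - 125".
- **Abnormality limits for vital signs**, introduced by "The following clinically relevant abnormalities, measured at rest, will be defined for vital signs", for 0-3 months, 3-12 months, 1-2 years and 2 to <3 years: "Heart rate HR (bpm) abnormally low <80 <70 <60 <90" on the low side and "abnormally high >180 >150 >140 >130" on the high side.
- **ECG limits**, including the RR interval: <333 and >750 ms at 0-3 months, <400 and >860 ms at 3-12 months, <430 and >1000 ms at 1-2 years, and <600 and >1200 ms at 2 to <18 years.

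Section 11.5 (Safety Analyses) says what is reported: "The percentage of subjects with values beyond clinically relevant limits". That sentence goes on to leave the definition of the limits to the SAP. For ECG, Section 11.5 plans frequency tables of abnormalities, and Attachment 2 plans a listing of the important ones.

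**The concern.** Limits that differ by age are expected. What stands out is that the heart-rate row runs downward with age and then turns upward at the second birthday, far enough that nearly half of the preceding class's normal range becomes abnormal. The same attachment also holds a second rule for the same quantity, because an RR interval is a heart rate in other units. That rule keeps moving in the original direction at age 2.

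If both tables are programmed as printed, one child with one heart rate at one visit can be normal in the vital-sign summary and abnormal in the ECG listing, or the other way round. The drug carries an important potential risk of QT prolongation (Section 1.2.4), so readers will look closely at the cardiac safety tables and should not have to reconcile two rules themselves. Age-adjusted normal heart rate also enters the clinical-stability endpoint in hospitalized subjects (Section 2.1.2). The protocol does not name the source of those normal values, but Attachment 2 is the only place where it prints any.

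**Working it through.** All inputs come from Attachment 2. There is no sample-size or power figure to reproduce.

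**Step 1. Normal range against the neighbouring class's abnormality limits.** For each parameter, every integer in a class's normal range was compared with the low and high limits of the same class and of the adjacent classes.

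- Within the same class, no normal value is flagged, for any parameter.
- Between adjacent classes there is exactly one overlap in the whole vital-sign table: heart rate, 1-2 years against 2 to <3 years. The normal range 70-110 has 110 - 70 + 1 = 41 integers. The limit <90 flags 70 to 89, which is 20 integers, and 20/41 = 49%.
- The direction is also out of line. The low limit goes <80, <70, <60, then <90. The normal range goes 100-150, 90-120, 80-120, 70-110, then 95-125.

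**Step 2. Vital-sign heart-rate limits against ECG RR limits.** Heart rate in bpm = 60000 / RR interval in ms, so a long RR limit gives a low heart-rate limit and a short one gives a high limit.

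| Age class | RR limits (ms) | Same limits as heart rate (bpm) | Vital-sign heart-rate limits (bpm) |
|---|---|---|---|
| 0-3 months | >750, <333 | <80.0, >180.2 | <80, >180 |
| 3-12 months | >860, <400 | <69.8, >150.0 | <70, >150 |
| 1-2 years | >1000, <430 | <60.0, >139.5 | <60, >140 |
| 2 to <3 years (RR class runs to <18 years) | >1200, <600 | <50.0, >100.0 | <90, >130 |

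In the first three rows the two rules differ by at most 0.5 bpm (140 - 139.5). In the last row they differ by 40 bpm on the low side (90 - 50) and 30 bpm on the high side (130 - 100).

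**Step 3. What the last row does to a child aged 2 to <3 years.**

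- 50-89 bpm: abnormally low as a vital sign, not flagged on RR.
- 90-100 bpm: flagged by neither.
- 101-125 bpm: within the stated normal range as a vital sign, abnormal on RR. The normal range 95-125 has 31 integers, and 25 of them (101 to 125) are flagged on ECG.
- 126-130 bpm: above the normal range but not flagged as a vital sign, abnormal on RR.
- Below 50 or above 130 bpm: flagged by both.

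Between 50 and 130 bpm, the two rules therefore agree only over 90-100 bpm.

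**The case against.** The best case against the point has four parts.

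*Age classes exist so that limits can differ, and each vital-sign class is consistent within itself.* The second half is correct for the vital-sign tables, and the 70-89 bpm overlap alone would be weak evidence. It does not answer Step 2, where two rules for the same class and the same quantity disagree after agreeing in every younger class.

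*Section 11.5 leaves the reported limits to the SAP.* This stands. The SAP is not shown and may already differ, so the protocol does not by itself fix the reported percentages. Section 11.5 also names heart rate, not RR, among the ECG variables to be presented, so how far the RR flag travels beyond the Attachment 2 listing is not settled. The contradiction in the printed limits remains.

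*The consequence is small.* This largely stands. Safety is descriptive, observed values and changes from baseline are summarized as well, and every arm is judged by the same limits. Treatment discontinuation for QT rests on a confirmed QTcF value (Sections 9.3.1 and 10.3), not on a heart-rate flag.

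*The other vital signs are sound.* A reader might infer from the abrupt steps at age 2 that respiratory rate and blood pressure contradict themselves too. They do not. The 1-2 year normal ranges (respiratory rate 20-30, systolic 90-105, diastolic 55-70) all escape the 2 to <3 year flags (<20 or >35, <80 or >110, <40 or >70). Oxygen saturation has one limit for all ages.

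**Conclusion.** The point holds for heart rate in the 2 to <3 year class and for nothing else in the vital-sign table. As printed, 70-89 bpm (20 of the 41 integers in the 1-2 year normal range) turns from normal to abnormally low at the second birthday. In addition, the vital-sign and ECG limits for ages 2 to <3 years classify 50-89 bpm and 101-125 bpm in opposite ways. The only assumption is the identity between RR interval and heart rate.

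The fractions above are shares of integer values, not of children or measurements. A reader might go on to infer that abnormality counts in this age group will be spurious, or that the comparison between arms is biased. The protocol supports neither. It gives no heart-rate distribution, and it guarantees only a subcohort of 6 subjects aged >2 to ≤3 years. Further enrolment at that age is open in Cohort 1 and conditional on committee review in Cohort 2. The same limits also apply to all arms. The size of any effect on the reported percentages therefore cannot be computed. This is a minor, cheaply corrected inconsistency in a safety definition.

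**What to change.** Reconcile three entries for ages 2 to <3 years in Attachment 2: the heart-rate normal range, the heart-rate abnormality limits and the RR limits. They should agree with one another, as they do in the younger classes, and any reversal against the 1-2 year class should be either removed or explained. Which limits are clinically right is the sponsor's decision; this review proposes none.

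Carry the reconciled limits into the SAP, to which Section 11.5 delegates the reported percentages, before any flags are derived. The cost is a corrected table and reprogrammed flags, with no new data. The respiratory-rate, blood-pressure and oxygen-saturation limits need no change on this ground.
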